Participants who develop any of the sight-threatening complications of DR in the Study Eye that are described in Table 3 will be treated with open-label KSI-301 5 mg, irrespective of the treatment group that they were originally randomized into (KSI-301 5 mg or sham). The original treatment group randomization will remain masked throughout the study.

At the visit that a sight-threatening complication of DR (DME, PDR and/or ASNV) is diagnosed (i.e., the "Dx Visit"), treatment with open-label KSI-301 5 mg will be initiated. Starting at the Dx Visit, participants will no longer follow the study visits and assessments outlined in Section 1.3.1 (SoA-A), nor receive further masked treatments. Instead, they will follow the study visits and assessments outlined in Section 1.3.2 (SoA-B), which is specific to the participants who develop DME, PDR, and/or ASNV.

As shown in Figure 2, treatment of DME, PDR, and/or ASNV will consist of the following:

 Two doses of KSI-301 5 mg, given four weeks apart (+/- 7 days), followed by KSI-301 5 mg once every 12 weeks (Q12W; +/-14 days). Thus, the first dose shall occur during the study visit in which DME, PDR, and/or ASNV was diagnosed, and the second dose shall occur 4 weeks (+/- 7 days) later. Thereafter, subsequent doses shall occur Q12W (+/-14 days).

More frequent visits and more frequent treatments with KSI-301 5 mg and/or panretinal photocoagulation (PRP) are at the discretion of the Investigator if the sight-threatening complication(s) as described in Table 3 are still present. Treatment with KSI-301 5 mg may not be given more often than monthly $(28 \pm 7 \text{ days})$.

End of Study Considerations

For participants who develop any of the sight-threatening complications described in Table 3, the following shall be considered:

- Participants shall not receive any treatment with KSI-301 5 mg after Week 92 (i.e., 92 weeks after the day of randomization (Day 1)).
- Weeks 96 and 100 (relative to the day of randomization (Day 1)) include final safety assessments that are mandatory and shall also be conducted according to the SoA-B (Section 1.3.2).

Figure 2:Protocol KS301P106: Dosing Regimen by Week for All Participants
Who Develop Sight-threatening Complication(s) in the Study Eye

	Q4W (±	7 days)	C	12W (± 14 day	SE	SA	
Week	Dx Visit	Dx Visit + 4 Weeks	Dx Visit + 16 Weeks	Dx Visit + 28 Weeks		96	100 ^b
KSI-301 5 mg ^a							
KSI-301 5 mg via intravitreal injection							treatment Visit

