6.1 Study Intervention(s) Administered

Study interventions are summarized in Table 4. For full information regarding the administration of study intervention and the contents of the kit, refer to the Pharmacy Manual. The full instructions for administration of sham are also described in the Pharmacy Manual.

Table 4:Protocol KS301P106: Study Interventions

Group Name	А	В
Intervention Name	KSI-301 5 mg	Sham
Туре	Biological medicinal product	Sham
Dose Formulation	Sterile liquid for intravitreal injection in single-use vials	Empty vial
Unit Dose Strength(s)	mg/mL (based on antibody mass)	N/A
Dosage Level(s)	5 mg	N/A
Route of Administration	Intravitreal injection	Sham injection
Use	Experimental	Sham (to maintain study masking)
IMP and NIMP	IMP	NIMP
Sourcing	Provided centrally by the Sponsor	Provided centrally by the Sponsor
Storage	In the original packaging, as provided, until the time of use. Store at 2-8°C before use. Refer to Pharmacy Manual for additional instructions.	In the original packaging, as provided, until the time of use. Store at 2-8°C before use. Refer to Pharmacy Manual for additional instructions.
Packaging and Labeling	KSI-301 will be provided in vials that will be labeled as required per country requirement.	Sham will be provided in vials that will be labeled as required per country requirement.
Reconstitution and Handling	KSI-301 is an aqueous solution that is provided in vial and filled into a syringe by unmasked site personnel without reconstitution or dilution.	Sham is provided as empty glass vials, which will remain empty throughout the sham treatment procedure. A sham injection mimics an intravitreal injection. It involves pressing the blunt end of an empty syringe, without a needle, against an anesthetized eye.
Current/Former Name(s) or Alias(es)	N/A	N/A

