5.2 Standard Calculations

Where appropriate, the calculated study day will be presented with the assessment or event date on subject data listings. Study day will be determined as:

- The assessment/event date minus the date of first dose of study drug, if the assessment/event date is prior to the date of first dose; and
- The assessment/event date minus the date of first dose of study drug, plus one, if the assessment/event date is on or after the date of first dose.

Start and stop dates will be imputed when partial dates are present as needed, to determine treatment emergent events and concomitant medications/procedures. No imputations will be done for a completely missing start/stop date or for subjects who did not receive study treatment.

Start dates with a missing day but with month and year available will be imputed such that:

- If the provided month and year match the month and year for that subject's first dose date, then the Day 1 date will be used.
- In all other cases the 1st of the month will be used with the provided month and year.

Start dates with a missing day and month but with available year will be imputed such that:

- If the provided year matches the year for that subject's first dose date, then the first dose date will be used.
- In all other cases the 1st of January will be used with the provided year.

Stop dates will be imputed as follows:

- Missing day with a provided year and month will use the last day of the month.
- Missing day and month with provided year will use December 31.

If the imputed stop date is greater than the last study date for the subject, then the imputed date will be replaced with the last available event date for the subject in the study.

Other variables requiring calculations will be derived using the following formulas:

- Days: A duration between two dates expressed in days will be calculated using the following conventions:
 - Later date earlier date + 1.
- Months: A duration expressed in months will be calculated by dividing the duration in days by (365.25 /12).
- Years: A duration expressed in years will be calculated by dividing the duration in days by 365.25.

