8.2 Adverse Events

Adverse events (AEs) will be coded to a MedDRA version 23.1 or later. AEs and Serious AEs (SAEs) will be summarized and listed by ocular events for the treated eye (or study eye), ocular events for the non-treated eye (or fellow eye), and non-ocular (systemic) events.

Treatment emergent AEs (TEAEs) are events with onset date on or after the initiation of study treatment through the last dose date of study treatment + 28 days, start date of non-study anti-

VEGF in study eye on or after last dose date, or start date of open-label KSI-301 treatment due to development of sight-threatening complication, whichever occurs first.

If the severity score of an adverse event is missing, the severity score will be imputed as severe. If the relatedness of an adverse event is missing, the adverse event will be considered related.

At each level of summarization (e.g., any AE, system organ class, and preferred term), subjects experiencing more than one TEAE will be counted only once. In the summary of TEAEs by severity grade, subjects will be counted once at the highest severity reported at each level of summarization.

Frequency tables including patients' incidence rates will be provided through Week 48 for the following:

- Ocular TEAEs and treatment-emergent serious AEs (TESAEs) (study eye and fellow eye separately)
- Non-ocular TEAEs and TESAEs
- Ocular TEAEs leading to study treatment discontinuation (study eye and fellow eye separately)
- Ocular TEAEs by severity (study eye and fellow eye separately)
- Non-ocular TEAEs by severity
- Related ocular TEAEs (study eye and fellow eye separately) by severity
- Related non-ocular TEAEs by severity
- Intraocular inflammation TEAEs and TESAEs not associated with infection, autoimmunity, drug toxicity, or traumatic etiologies (study and fellow eye separately).
- IOI TEAEs and TESAEs associated with infection (study and fellow eye separately).
- IOI TEAEs and TESAEs associated with autoimmune, drug toxicity, or trauma (study and fellow eye separately).
- Arteriothromboembolic (ATE) Adverse Events. ATEs will be tabulated as those events meeting the Anti-Platelet Trialists' Collaboration criteria (i.e., nonfatal

myocardial infarction, nonfatal stroke, and vascular death, including deaths of unknown cause)

- Adverse events of special interest [AESI] (study eye, fellow eye and non-ocular combined), as defined in the protocol Section 8.3.6
- Injection procedure related TEAEs and TESAEs in study eye

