- Non-serious TEAEs and TESAEs (study eye, fellow eye and non-ocular combined)

All AEs and serious AEs will be presented separately in data listings by treatment group, subject ID, and event date. Adverse events from patients who remain in the study after study treatment discontinuation will be listed.

For subjects who receive open-label KSI-301 5mg treatment due to development of sightthreatening complications, ocular TEAEs and TESAEs for study eye starting from when subjects switch to open-label KSI-301 treatment will be summarized until the end of study. All AEs (study eye, fellow eye and non-ocular) will be presented in a data listing by subject ID, and event date.

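### A same-day adverse event of a sham participant's first open-label KSI-301 injection can count as a sham TEAE and again in the open-label summary; how often depends on an undefined last-dose term

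*SAP*

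**What the plan says.** **TEAE window (SAP 8.2).** TEAEs are "events with onset date on or after the initiation of study treatment" "through the last dose date of study treatment + 28 days", or until non-study anti-VEGF is started in the study eye, "or start date of open-label KSI-301 treatment due to development of sight-threatening complication, whichever occurs first". The rule is written in dates. It does not ask whether onset came before or after an injection on the closing day.

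**Open-label summary (end of SAP 8.2).** For participants who switch, study-eye ocular TEAEs and serious TEAEs "starting from when subjects switch to open-label KSI-301 treatment will be summarized until the end of study". The switch day is not excluded.

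**Timing of the switch (Protocol 4.1.3.1).** At the visit where DME, PDR or ASNV is diagnosed, "treatment with open-label KSI-301 5 mg will be initiated"; that is, "the first dose shall occur during the study visit in which DME, PDR, and/or ASNV was diagnosed". No masked dose is given from that visit on.

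**Sham procedure (Protocol 6.1, Table 4).** Sham consists of "pressing the blunt end of an empty syringe, without a needle" against an anesthetized eye.

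**Partial AE dates (SAP 5.2).** An unknown start day becomes the first-dose date if month and year match the first dose. "In all other cases the 1st of the month will be used with the provided month and year".

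**Which doses are study treatment.** SAP 8.2 does not say. SAP 8.1 leaves open-label KSI-301 out of the study-medication exposure summary, which points to masked doses only. Protocol 6.0 defines study intervention broadly enough to include open-label doses. SAP 5.4.2 analyzes safety by treatment received but has no rule for participants who switch.

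**The concern.** On the switch day a sham participant receives the first needle injection of KSI-301 that the protocol gives to that eye. Protocol 8.1.4 and SoA-B require a vision check and tonometry after it, so a same-day pressure rise or similar event is likely to be found and dated to that day. If that day is inside the masked window, an event caused by KSI-301 appears in the sham rows for ocular, related and injection-procedure-related TEAEs.

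At stake is the descriptive safety contrast. Moving KSI-301 injection events into the sham rate narrows the difference between arms. If KSI-301 prevents complications, more sham than KSI-301 participants switch, and the effect falls mainly on the sham side. The same study-eye event can also appear a second time in the open-label summary.

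**Working it through.** The plan states no figure on this point, so the check is date arithmetic on the SAP 8.2 rule.

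**1. The rule.** Window end = min(last dose + 28 days; start of non-study anti-VEGF; start of open-label KSI-301), with the end day included. A switch-day event is a sham TEAE if the open-label start is on or before the other two dates. Below, no non-study anti-VEGF is assumed.

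**2. Broad reading: open-label doses count as study treatment.** The last dose is then on or after the open-label start, so last dose + 28 days always falls later than that start. The open-label start closes the window, and its day is included. A same-day event is a sham TEAE at every switch.

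**3. Narrow reading: masked doses only.** Inputs are the scheduled study days in SAP Table 3, the masked dosing visits in Protocol 4.1.3 (Day 1, Weeks 8, 20, 44) and the visit windows in SoA-A. Gap = day of diagnosis visit minus day of last masked dose.

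| Diagnosis visit | Last masked dose | Nominal gap (days) | Range with visit windows | Gap of 28 or less? |
|---|---|---|---|---|
| Week 8 | Day 1 | 56 − 1 = 55 | 48 to 62 | No |
| Week 20 | Week 8 | 140 − 56 = 84 | 63 to 105 | No |
| Week 32 | Week 20 | 224 − 140 = 84 | 56 to 112 | No |
| Week 44 | Week 20 | 308 − 140 = 168 | 140 to 196 | No |
| Week 48 | Week 44 | 336 − 308 = 28 | 7 to 49 | Nominally yes, exactly |

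At Weeks 8, 20, 32 and 44 the window has already closed. At Week 48 the gap is 28 + b − a, where a (−14 to 14) and b (−7 to 7) are the deviations of the Week 44 dose and the Week 48 visit. The event counts when b ≤ a, which holds for 225 of 29 × 15 = 435 date pairs (52% if all pairs were equally likely, an assumption). An unscheduled diagnosis within 28 days of a masked dose also counts. After Week 48, the gaps at Weeks 56, 68, 80 and 92 are 84, 168, 84 and 168 days, all outside even with visit windows.

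**4. Double counting.** The open-label summary starts at the switch, so a study-eye ocular event on that day meets both definitions whenever step 2 or step 3 admits it. Other events are only listed for the open-label period.

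**5. Size.** The documents give neither a switch rate nor a same-day event rate. Assume that 20–40% of 120 sham participants switch by Week 48 and that 10–20% of them have a same-day ocular event:
- Broad reading: 120 × 0.20 × 0.10 = 2.4 to 120 × 0.40 × 0.20 = 9.6 participants, or 2 to 8 percentage points.
- Narrow reading, if switches were spread evenly over the five visits above (illustrative): at most one fifth, 0.48 to 1.92 participants, or 0.4 to 1.6 points.

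**6. Partial dates.** An event after the switch whose day is unknown, in the switch month, is set to the 1st, at most 30 days before the switch. On the broad reading that places it inside the masked window. On the narrow reading the 1st must also lie within 28 days of the last masked dose. With nominal gaps, this is possible at Week 8 (55 − 30 = 25) and Week 48 (28 − 30 < 28), but not at Weeks 20 and 32 (84 − 30 = 54) or Week 44 (168 − 30 = 138). At the extreme of the visit windows Week 32 could just qualify (56 − 30 = 26).

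**The case against.** The strongest reply is that the earliest-of-three clause does most of the work. SAP 8.1 separates open-label KSI-301 from study medication, and SAP 8.2 names it as its own limiter, so masked doses only is a natural reading. Most scheduled switches then fall after the window has closed. This stands, and it rules out the inference that every sham switch contaminates the sham tables. It does not settle the matter. On that reading the open-label limiter would hardly ever act at a scheduled visit, and Protocol 6.0 supports the broad reading. Two programmers could produce different sham tables from the same text.

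Other replies also have force:
- **Sham is not a pure no-injection reference.** Protocol 8.1.3 recommends subconjunctival anesthesia and holds the method constant across masked visits, so the sham procedure can itself cause conjunctival hemorrhage or pain.
- **The assumed size is generous.** Participants are counted once per level, not every same-day ocular event is injection-related, and switch-day events in KSI-301 participants partly offset the narrowing.
- **The events are not lost.** They appear in the dated listings and the open-label summary. A reader might infer that they are hidden; the documents do not support that.
- **Including the switch day has a purpose.** The complication diagnosed before the injection belongs to the masked period, so dropping the whole day would lose it.
- **The tables are descriptive.** No hypothesis test depends on them.

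**Conclusion.** The point holds in limited form. SAP 8.2 includes the switch date in the masked window without separating what precedes the first open-label injection from what follows it, and the open-label summary starts at the same point. One event can therefore be attributed to sham and also counted under open-label KSI-301.

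The frequency turns on the undefined last-dose term: potentially every switch if open-label doses count (barring earlier non-study anti-VEGF), or Week 48 and unscheduled diagnoses within 28 days of a masked dose if they do not. A reader might take 2 to 8 points as the expected bias. The documents do not support that: the inputs are assumed, and the range is an upper one for the broad reading. The narrow reading gives less. The correction is still worth making, because it is cheap and the misattributed events raise the sham rate.

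**What to change.** In SAP 8.2:

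1. State whether the last dose date of study treatment means masked doses only or all doses.
2. End the masked TEAE window the day before the first open-label injection, and assign each onset on the switch date to one period only. Study-eye events judged related to the injection procedure or to open-label KSI-301 go to the open-label period. The qualifying DME, PDR or ASNV and unrelated events stay in the masked period, subject to the same 28-day limit.
3. For AEs with an unknown day in the switch month, apply the same relatedness rule and cross-refer from SAP 5.2. Do not impute the switch date for all of them, since that would move genuine pre-switch events into the open-label period.

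The rule should not depend on AE onset time. Protocol 6.4 records the time of each dose, but the documents do not say that AE onset time is recorded. Relatedness to the procedure or study intervention is already assessed for each AE (Protocol 10.3.3).

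The cost is a few sentences and a small programming change. A few events move from the sham tables to the open-label table. Assignment on the switch date then rests on investigator causality, and the SAP 8.2 convention that missing relatedness counts as related would send such study-eye events to the open-label period.

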1.3.2 SoA-B

The following schedule of activities, SoA-B, shall be followed once a participant is diagnosed with sight-threatening complication(s) of DR, as defined in Table 3 (Section 4.1.3.1), in their Study Eye. Upon diagnosis of sight-threatening complication(s) of DR in their Study Eye, participants will be treated with open-label KSI-301 5 mg, regardless of the treatment group that they were originally randomized into, and SoA-B will be followed instead of SoA-A. Additional details are provided in Section 4.1.3.1.

Visit	Dx Visit ¹	Dx Visit + 4 Weeks	Dx Visit + 16 Weeks	Dx Visit + 28 Weeks	Dx Visit + 40 Weeks	Dx Visit + [] ¹² Weeks	Week 96/ET	Week 100 ¹³
Visit Windows (Days)		+/-7	+/-14	+/-14	+/-14	+/-14	+/-7	+/-7
Concomitant Medication Review ²	Х	Х	X	Х	Х	Х	Х	X
AE/SAE Review	Х	Х	X	Х	X	Х	Х	X
General Assessments								
Vital Signs ³							Х	
Laboratory ⁴							Х	
Plasma ADA/NAB Samples (pre-injection)	Х			Х			Х	
Plasma PK/Biomarker Samples (pre- injection)	Х			Х			Х	
Pregnancy Test ⁵ (WOCBP only)	Х	Х	X	Х	Х	Х	Х	Х
Ophthalmic Assessments ⁶								
BCVA ETDRS (4 meters) ⁷	Х	Х	X	Х	X	Х	Х	
Ophthalmic Exam (Slit lamp, IOP ⁸ , dilated indirect ophthalmoscopy)	Х	Х	X	Х	Х	Х	Х	
SD-OCT ⁹	Х	Х	X	Х	Х	Х	Х	
Fundus Photos ⁹	Х	Х	X	Х	Х	Х	Х	
Fluorescein Angiogram ⁹	Х			Х			Х	
KSI-301 5 mg (Open-label) ¹⁰	Х	Х	X	Х	X	Х		
Post-injection Assessments (Vision check, IOP ⁸) ¹¹	Х	Х	X	Х	Х	Х		

- Abbreviations: ADA = anti-drug antibody; AE = adverse event; ASNV = anterior segment neovascularization; BCVA = best corrected visual acuity; Dx Visit = the first study visit where a sight-threatening complication of diabetic retinopathy (DME, PDR, and/or ASNV) is diagnosed; DME = diabetic macular edema; ET=Early Termination; ETDRS = early treatment diabetic retinopathy study; IOP = intraocular pressure; NAB = neutralizing antibody; PK = pharmacokinetics; PDR = proliferative diabetic retinopathy; Q12W = once every 12 weeks; SAE = serious adverse event; SD-OCT = spectral domain optical coherence tomography; WOCBP = women of childbearing potential.
- ¹ Dx Visit is the first study visit where a sight-threatening complication of diabetic retinopathy (DME, PDR, and/or ASNV, as defined in Section 4.1.3.1) is diagnosed in the Study Eye; open-label KSI-301 treatment will be initiated at this visit.
- ² Record any concomitant medication used by the participant within 30 days prior to Day 1. Procedural medications administered (e.g., dilating drops, fluorescein) will not be recorded.

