- ³ Height and weight will be recorded at the screening visit only.
- ⁴ Clinical laboratory tests as described in Appendix 2 and Table 5.
- ⁵ Urine pregnancy test will be performed locally for women of childbearing potential, prior to fluorescein angiogram and study treatment (if applicable). If urine pregnancy test is positive, it must be confirmed with a serum pregnancy test. Local urine testing will be standard for the protocol unless serum testing is required by local regulation or IRB/IEC.
- ⁶ Ophthalmic assessments will be performed in both eyes at Week 96, and only in the Study Eye at all other timepoints.
- ⁷ Perform BCVA before any other ophthalmic assessments and prior to dilation.
- ⁸ Method used to measure IOP must remain consistent throughout study.
- ⁹ It is mandatory that the same model of device is used for the entire duration of the study.
- ¹⁰ Participants who discontinue study treatment should NOT be considered withdrawn from the study. Additional details are provided in Section 7.1.
- ¹¹ Post injection assessments include vision check for counting fingers and tonometry. The post-injection assessments should be performed by unmasked assessors.
- ¹² Continue visits Q12W until Week 92.
- ¹³ Week 100 is a final safety assessment that will be done via telephone call for all participants, except in WOCBP, in which case a site visit is required for the safety assessment that includes a pregnancy test.

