3.0 OBJECTIVES AND ENDPOINTS

Objectives	Endpoints				
Primary					
To demonstrate that KSI-301 5 mg is superior to sham treatment, with respect to proportion of eyes improving ≥ 2 steps on DRSS from baseline at Week 48.	• The proportion of eyes improving ≥2 steps on DRSS from baseline at Week 48.				
Secondary					
To evaluate the effect of KSI-301 5 mg in decreasing the incidence and delaying the onset of vision- threatening complications of diabetes compared to above tractment	• Time to development of and proportion of eyes developing any of the following from baseline over time (individually and as a composite):				
sham treatment.	- PDR or ASNV;				
	 Vitreous hemorrhage or tractional retinal detachment believed to be due to proliferative diabetic retinopathy; or 				
	- DME.				
To evaluate the efficacy of KSI-301 5 mg compared to sham treatment.	 Proportion of eyes improving ≥2 or ≥3 steps on DRSS from baseline over time. 				
	 Proportion of eyes worsening ≥2 or ≥3 steps on DRSS from baseline over time. 				
To evaluate the safety and tolerability of KSI-301 5 mg compared to sham treatment.	• Incidence of ocular and systemic adverse events over time.				
To assess the systemic pharmacokinetics (exposure)	Systemic pharmacokinetic profile over time.				
and immunogenicity of KSI-301.	• Systemic anti-drug antibody status over time.				
Exploratory					
Additional exploratory endpoints will be further describe	d in the SAP.				

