2.0 STUDY OBJECTIVES AND ENDPOINTS

Table 1 lists the primary, key secondary and additional secondary study objectives, along with their corresponding endpoints.

Table 1: Objectives and Endpoints

Table 1: Objectives and Endpoints Objectives	Corresponding Endpoints
	Corresponding Endpoints
Primary To demonstrate that KSI-301 5 mg is superior to sham treatment, with respect to proportion of eyes improving ≥2 steps on Diabetic Retinopathy Severity Scale (DRSS) from baseline at Week 48.	• The proportion of eyes improving ≥2 steps on DRSS from baseline at Week 48.
Key Secondary	
To demonstrate that KSI-301 5 mg is superior to sham treatment, with respect to proportion of eyes with vision-threatening complications of diabetes, and proportion of eyes improving \geq 3 steps on Diabetic Retinopathy Severity Scale (DRSS).	 Proportion of eyes developing any of the following from baseline through Week 48: PDR or ASNV; Vitreous hemorrhage or tractional retinal detachment believed to be due to PDR; or DME.
	• Proportion of eyes improving ≥3 steps on DRSS from baseline at Week 48.
	• Proportion of eyes developing PDR through Week 48.
Additional Secondary	
To evaluate the efficacy of KSI-301 5 mg compared to sham treatment.	• Proportion of eyes developing PDR or ASNV from baseline through Week 48.
	• Proportion of eyes developing vitreous hemorrhage or tractional retinal detachment, believed to be due to PDR, from baseline through Week 48.
	• Proportion of eyes developing DME from baseline through Week 48.
	• Proportion of eyes with a ≥2-step worsening from baseline on DRSS from baseline at Week 48.
	• Proportion of eyes with a ≥3-step worsening from baseline on DRSS from baseline at Week 48.
	• Time to first development of PDR, ASNV, or DME through Week 48.
	• Time to first development of PDR or ASNV through Week 48.
	• Time to first development of vitreous hemorrhage or tractional retinal detachment, believed to be due to PDR through Week 48.
	• Time to first development of DME through Week 48.
	• Mean change in SD-OCT central subfield thickness (CST) from baseline by visit over time.
	• Mean change in BCVA from baseline by visit over time.
	• Proportion of eyes who lose ≥ 5 , ≥ 10 , or ≥ 15 letters in BCVA from baseline by visit over time.

KS301P106 SAP Version 1.0 KSI-301 – Kodiak Sciences Inc.

Objectives	Corresponding Endpoints
To evaluate the safety and tolerability of KSI-301	Incidence of ocular and systemic adverse events up to Week 48.

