5.0 GENERAL STATISTICAL METHODS

SAS (SAS Institute Inc., Cary NC, USA) Version 9.4 or higher will be used for the study analyses.

5.1 **Reporting Conventions**

Tables and figures will be summarized by treatment group. Tables summarizing demographics and other baseline characteristics will also include a column for all patients combined. In general, all data collected and any derived data will be presented in subject data listings, for all randomized patients. Listings will be ordered by treatment group, subject number, and assessment or event date. The treatment groups will be displayed in the same order as the summary tables. The treatment groups presented in listings will be based on the planned assignment, unless otherwise noted.

In general, continuous variables will be summarized to indicate the study population sample size (N), number of subjects with available data (n), mean, SD, median, 25th (Q1) and 75th (Q3) quartiles, minimum, and maximum values. Categorical variables will be summarized by the population size (N), number of subjects with available data (n), number of subjects in each category, and the percentage of subjects in each category. Unless otherwise noted, the denominator to determine the percentage of subjects in each category will be based on the number of subjects with available data. The denominator for percentages for incidence data (such as adverse events) will be based on the number of subjects in the analysis population "at risk." Select ordinal data may be summarized using both descriptive statistics and counts and percentages of subjects in each category, as appropriate.

Non-zero percentages will be rounded to one decimal place. Percentages that round down to 0 or up to 100% will be displayed as "<0.1%" and ">99.9%", respectively. Rounding conventions for presentation of summary statistics will be based on the precision of the variable of summarization, as it is collected in its rawest form e.g., on the electronic case report form (eCRF) and are outlined as follows:

- The mean and median will be rounded to an additional decimal place than the precision of the variable of summarization;
- Measures of variability (e.g., SD, SE) will be rounded to two additional decimal places than the precision of the variable of summarization; and
- Minimum and maximum values will be presented using the same precision as the variable of summarization.

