8.0 SAFETY EVALUATION

Safety analyses will be performed for the Safety Analysis Set. In the Primary Analysis, safety data from Day 1 to Week 48 will be summarized by treatment group.

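### Crude TEAE percentages through Week 48 compare unequal time at risk if sham participants switch to open-label KSI-301 more often or earlier; no person-time rate is planned beside them

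*SAP*

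**What the plan says.** SAP 2.0 (Table 1) names the safety endpoint for the comparison with sham: "Incidence of ocular and systemic adverse events up to Week 48". SAP 8.0 says that "safety data from Day 1 to Week 48 will be summarized by treatment group".

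SAP 8.2 defines TEAEs as "events with onset date on or after the initiation of study treatment through the last dose date of study treatment + 28 days", with two earlier stopping points: non-study anti-VEGF in the study eye, and the "start date of open-label KSI-301 treatment due to development of sight-threatening complication, whichever occurs first". Each subject counts once per term. On the denominator, SAP 5.1 says: "The denominator for percentages for incidence data (such as adverse events) will be based on the number of subjects in the analysis population" at risk. That is a head count, not person-time.

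The switch can happen in either arm. Protocol 1.3.2 (SoA-B) says that at the diagnosis visit "open-label KSI-301 treatment will be initiated at this visit". Protocol 3.0 gives as a secondary objective "decreasing the incidence and delaying the onset of" these complications relative to sham, and the first key secondary endpoint (SAP 7.2.1) is the proportion of eyes that develop one by Week 48.

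After the switch, SAP 8.2 summarises study-eye ocular events only; fellow-eye and non-ocular events are listed. SAP 8.1 summarises injections and duration of exposure by arm but does not use them as a denominator for adverse events. Protocol 9.4.5 plans per-injection rates for certain events. SAP Section 8 does not include them, and SAP 10.0 does not mention the change, although SAP 1.0 says that changes from the protocol will be explained there.

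**The concern.** If KSI-301 works as hypothesised, more sham participants leave the window early. An event that happens after they leave cannot count, yet they remain in the denominator. Two arms with the same underlying event rate would then show different percentages, in a direction that the trial's own hypothesis predicts.

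The affected tables include systemic events, serious events and arterial thromboembolic events, which are the core of the safety comparison with sham. A non-ocular event after the switch enters neither the TEAE table nor the post-switch summary; it appears only in a listing. The data exist, because switchers stay in follow-up and adverse event review continues at every SoA-B visit. The gap is in the tabulation.

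**Working it through.** **Inputs from the documents.** The reporting period is 48 weeks, with about 120 participants per arm (SAP 9.0). A participant who stays on masked treatment is covered to Week 48, because the Week 44 dose plus 28 days reaches it. A switcher's window is taken to end at the switch. The plan states no figure on this point, so there is none to reproduce.

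**Assumptions.** Neither document gives switch rates or event rates. I take 5–10% switching on KSI-301 and 20–40% on sham, and vary the timing. The base case is 10% against 30%, all at Week 24.

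**Step 1: time at risk.** Mean weeks = (1 − s) × 48 + s × t, where s is the share switching and t the week of the switch.

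| Switching KSI-301 / sham | Switch week | KSI-301 weeks | Sham weeks | Ratio |
|---|---|---|---|---|
| 10% / 30% (base) | 24 | 0.9×48 + 0.1×24 = 45.6 | 0.7×48 + 0.3×24 = 40.8 | 1.12 |
| 10% / 20% | 30 | 46.2 | 44.4 | 1.04 |
| 5% / 40% | 24 | 46.8 | 38.4 | 1.22 |
| 5% / 30% | 44 | 47.8 | 46.8 | 1.02 |
| 5% / 30% | 8 | 46.0 | 36.0 | 1.28 |
| 5% / 5% | any | equal | equal | 1.00 |

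With mid-period to late switching the ratio is about 1.02 to 1.22. Switches concentrated at the first visits would push it higher. In the base case, multiplying by 120/52.18 gives 104.9 against 93.8 patient-years.

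**Step 2: effect on the crude percentage.** Give both arms the same constant hazard, λ = −ln(1 − risk)/48. Then crude % = (1 − s)(1 − e^(−48λ)) + s(1 − e^(−tλ)).

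- Risk 5%: λ = 0.001069 per week. The crude percentages are 4.75% against 4.26%, a difference of 0.49 points, or 5.70 against 5.11 participants per 120. The standard error of the difference, √(p₁q₁/120 + p₂q₂/120), is 2.68 points.
- Risk 40%: λ = 0.01064 per week. The crude percentages are 38.25% against 34.76%, a difference of 3.49 points, with standard error 6.21.

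For the second and third rows of the table (1.04 and 1.22) the differences are 0.18 to 0.86 points at 5% risk and 1.27 to 6.11 points at 40% risk.

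**Step 3: the person-time rate.** The rate to first event is λ × 52.18 × 100: 5.58 and 55.5 per 100 patient-years respectively, the same in both arms.

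**Step 4: a counter-case.** Suppose all the risk of a rare event falls in the first 8 weeks, before any base-case switch. The crude ratio is then a correct 1.00, while the patient-year rate ratio is 40.8/45.6 = 0.89. For such events the rate misleads and the percentage does not.

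**Step 5: injections.** Spread the 10% and 30% of switches evenly over the Week 8, 20, 32 and 44 visits (mean Week 26, so not the base-case timing). Masked doses before the switch are 1, 2, 3 and 3, mean 2.25, against 4 for a participant who does not switch. The means are 0.9×4 + 0.1×2.25 = 3.83 and 0.7×4 + 0.3×2.25 = 3.48, or 459 against 417 injections. A per-injection rate would use this denominator.

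**The case against.** The strongest reply is that the effect is conditional, small and partly visible already. In the base case it lies well inside sampling error. The SAP names no hypothesis test for adverse events, so the tables are descriptive. The exposure summary and the listings show the unequal follow-up, and deaths are listed by treatment group. Ending the window when everyone moves to the active drug is defensible. All of this stands, and it is why the point is a supplement to the tables and not the repair of an error.

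The reply also says that a patient-year rate is not a cure. The switch is triggered by disease worsening, so the censoring is informative and person-time does not remove that. Early or injection-clustered events fit the rate poorly. Both points stand and limit what the added rate can claim.

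The documents do not support four stronger inferences that a reader might draw.

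- That the tables hide harm from the drug. With equal, roughly constant hazards and more switching on sham, the distortion runs against KSI-301.
- That no exposure-based rate was ever planned. Protocol 9.4.5 plans per-injection rates; person-time rates are what both documents lack.
- That the open-label limit could never take effect if the last dose meant masked doses only. At nominal visit days the 28-day limit does come first or ties, but the visit windows allow otherwise. A Week 44 dose on day 322 gives a limit of day 350, and a Week 48 diagnosis on day 329 closes the window sooner.
- That a switcher's window is seriously ambiguous. Footnote 10 of SoA-B, attached to the open-label row, says: "Participants who discontinue study treatment should NOT be considered withdrawn from the study". So the protocol uses the term study treatment for open-label doses too, and the natural reading ends the window at the start of open-label treatment. Saying so is only a wording clarification.

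**Conclusion.** The point holds as a modest, conditional weakness in the safety summary. If sham participants switch more often or earlier, which the trial's own objectives expect, the planned percentages compare unequal time at risk, and neither document plans a person-time rate to set beside them.

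Under the assumed switching, the time-at-risk ratio is about 1.02 to 1.22 depending on timing. The base-case distortion is 0.5 points for a 5% event and 3.5 points for a 40% event, both smaller than one standard error. These figures rest on assumed switch rates and on equal, roughly constant hazards. With equal switching there is no distortion, and for events clustered early or after injections the direction need not hold.

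Separately, the protocol's per-injection rates are missing from SAP Section 8 without the explanation that SAP 1.0 promises. That is a gap in documentation and does not depend on any switch rate.

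**What to change.** **Main change.** In the TEAE tables by arm, keep the crude percentages and add the number of participants with an event per 100 patient-years, with a 95% CI. Time runs to the first event or the end of the TEAE window, capped at Week 48. A footnote should say that the rate assumes a roughly constant hazard, suits early or injection-clustered events poorly, and does not remove informative censoring from a switch triggered by disease worsening.

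**Supporting changes.**

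- Tabulate non-ocular adverse events, serious events and arterial thromboembolic events after the switch by randomised arm, so that all events to Week 48 can be summarised. This is an account of everything that happened in each arm, not a drug-against-sham contrast, since everyone receives KSI-301 after the switch.
- Restore the per-injection rates of Protocol 9.4.5, which suit injection-related events better, or record their omission in SAP 10.0.
- As wording only, state that a switcher's window runs to the start of open-label treatment, and give the post-switch summary a label other than TEAE, since the definition ends at the switch.

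**Cost.** One derived time-at-risk variable and a few tables from dates already collected. Data collection, the crude percentages and participant management do not change.
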